- Toxicity induced by TAE and or MWA using the latest published full version of Common Terminology Criteria for Adverse Events ([CTCAE v5.0](#) is slated for release in October 2015; [CTCAE v4.0](#) is available currently)
- 1-month and 3-month postoperative morbidity using the Clavien-Dindo Classification of Surgical Complications²⁷ (Appendix II);
- 1-month and 6-month postoperative mortality

- Ablation characteristics including tumor location by hepatic segment, proximity to a portal pedicle, number of applications, power settings, and ablation duration (per application and per tumor)
- Radiologic tumor observations applied to the Liver Imaging Reporting and Data System (LI-RADS) criteria at 4-6 weeks post-ablation, every 3 months for the first 2 years, and every 6 months thereafter
- AFP levels: baseline (preoperative/at diagnosis), 4-6 weeks post-ablation and TAE, every 3 months for the first 2 years, and every 6 months thereafter
- Return of bowel function (days), subdivided in: time until first stool, introduction of liquid or solid diet;
- Length of hospital stay (days);
- Length of ICU stay (days);
- 30- and 90-day readmission rates;
- Return to normal activity (days), i.e., return to full activity, work, or sport;
- Preoperative (baseline), 6-month and 1-year postoperative quality of life (QOL), using the Standard form 36 (SF-36 v 1.0) customized for HCC
- For those patients who go on to resection:
 - Duration of resection operation (minutes), defined as incision to dressing time;
 - Correspondence between pre-randomization clinical/radiologic/laboratory evaluation and intraoperative findings

Methods

Patient Eligibility and Allocation

Eligible patients will be identified in collaboration with the Levine Cancer Institute (LCI) at Carolinas Medical Center (CMC). The Institute functions as a series of integrated cancer programs distributing high-quality cancer care system-wide and houses nine cancer clinics, infusion therapy, palliative care and clinical trials, and state-of-the-art technology to connect member institutions across the Carolinas and worldwide. CMC is a high-volume center for the treatment of hepatocellular carcinoma and is one of only a few hospitals across the nation to utilize minimally invasive microwave ablative therapies to treat liver cancer. Approximately 60 MWA and several hundred TAE procedures are performed annually

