According to a computer-generated variable size blocked randomization method, eligible patients will be allocated on a 1:1 basis to receive the experimental therapy (MWA + TAE) and standard therapy (MWA alone), respectively. The nature of the treatments and their possible adverse effects preclude the use of double-blind and double dummy techniques. In patients randomized to receive the experimental therapy, TAE treatments will be initiated within one week of randomization, then followed by MWA within 4 to 6 weeks after reviewing radiological scans from TAE. MWA will be performed 4 to 6 weeks following randomization in MWA standard therapy groups. Treatment may be discontinued if any exclusion criteria develop in the patient or at the patient's request.

Sample Size

Power calculations are based upon expected 2-year survival rates. The main endpoint is 2-year intrahepatic disease-free survival, measured from the time of randomization which is measured from time of randomization and is defined as the absence of local or regional recurrence of HCC as determined by diagnostic imaging. Considering an estimated 80% and 90% intrahepatic disease-free survival at 2 years of follow-up for patients receiving MWA alone and MWA + TAE combination therapy, respectively, a sample size of 92 patients is required to detect a clinically meaningful 10% absolute difference in 2-year peritoneal disease-free survival with MWA + TAE with a minimum of 95% power and a 2-sided $\alpha = .05$. To account for a 5–10% withdrawal rate (following intraoperative detection of vascular invasion or extrahepatic metastasis, etc.), a sample size of 100 patients is required (50 patients per arm). If the rate of patient enrollment is suboptimal, a covariate adaptive randomization method will be used to allocate patients in a 2:1 ratio to receive experimental therapy (MWA + TAE) and standard therapy (MWA alone), respectively, which would result in an overall sample size of 83 patients.

Clinical Procedures

Preprocedural Strategy

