All operative MWAs will be performed in a laparoscopic or robot-assisted laparoscopic setting by one of four hepatobiliary surgeons with extensive experience with intraoperative US guidance and hepatic ablation ([name]). Care will be taken to create ample distance between the microwave near-field and any adjacent structures (diaphragm/heart, stomach/esophagus, colon, duodenum, gallbladder) by mobilization of the liver. All ablations will be guided by intraoperative ultrasound (BK Medical A/S, Herlev, Denmark) with care taken to allow for complete tumor treatment while preserving adequate distance between the microwave near-field and adjacent intrahepatic structures (portal pedicles, hepatic veins). Ablations will be performed with a 2.45-GHz generator with a 1.8-mm-diameter transcutaneous antenna (Acculis pMTA Accu2i; AngioDynamics Inc., Denmead, Hampshire, UK).

Operative variables will be recorded per patient, and individual ablation characteristics including tumor location by hepatic segment, proximity to a portal pedicle, number of applications, power settings, and ablation duration will be recorded for each individual tumor. A clearly demarcated zone of color flow Doppler activity will be visualized within 30 s of initiating the ablation to assure that the target is within the microwave ablation zone. Patients will be observed carefully, and analgesia will be administered per standard protocol if necessary.

Postprocedural Strategy

Division-specific standard guidelines will be applied to the postoperative care of patients included in this study. Postoperative complications will be recorded and treated symptomatically. All patients will be closely followed up for disease progression with clinical and laboratory examinations 4–6 weeks after ablation/TAE procedures, then every 3 months for the first 2 years. At 4–6 weeks following TAE +/- MWA procedures, tumors will be assessed radiographically and characteristics will be reported according to the LI-RADS criteria and guidelines. Imaging techniques will then be performed every 3 months during the first 2 years postoperative and every 6 months afterward. In addition, AFP levels will be obtained every 3 months during the first 2 years postoperative and every 6 months afterward.

Data Collection

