All parameters will be prospectively collected. The study will be approved by the Internal Review Board of Carolinas Medical Center, and informed consent will be obtained from all patients prior to study participation. All hepatocellular carcinomas will be classified according to the TNM criteria of the American Joint Commission on Cancer (AJCC) 2010 Cancer System. A comprehensive medical history will be obtained from each patient and supplemented by clinical notes. Pre-, intra-, and postoperative variables (Table 1) and clinical outcomes will be recorded in an electronic database. Toxicity induced by TAE and or MWA will be graded according to the [Common Terminology Criteria for Adverse Events - CTCAE v5.0](#) (Slated for release in October 2015; v4.3 available at <http://evs.nci.nih.gov/ftp1/CTCAE/About.html>).

Table 1. Variables for analysis

Patient characteristics	age, sex, viral hepatitis status, nicotine use, alcohol use, drug use, hypertension, obesity, diabetes mellitus, general conditions, prior therapy, underlying disease status as determined by Child-Pugh and MELD score
Preoperative imaging	presence of cirrhosis; tumor size, location and number
Intraoperative findings	surgeon performing procedures, proximity of tumor to portal pedicle, number of TAE applications, number of MWA applications, power settings, ablation duration (per application and per tumor), pathology from random liver biopsy
Postoperative data	Tumor radiology, length of stay, 30- and 90-day readmission, wound infection, postoperative complications (encephalopathy, liver failure, ascites, upper GI bleeding), postoperative Δ MELD score
Tumor characteristics	BCLC classification, Okuda stage, AJCC clinical tumor stage, venous infiltration, lymphatic infiltration
Laboratory data	α -fetoprotein (AFP) level, Hb, leukocytes, thrombocytes, serum proteins, albumin, bilirubin, γ -GT, ASAT, creatinine, INR, alkaline phosphatase

Abbreviations: MELD, Model for End-Stage Liver Disease; TAE, transarterial chemoembolization; MWA, microwave ablation; GI, gastrointestinal; BCLC, Barcelona Clinic Liver Cancer; AJCC, American Joint Committee on Cancer; Hb, hemoglobin; γ -GT, gamma-glutamyl transpeptidase; ASAT, aspartate amino transferase; INR, international normalized ratio.

Definitions

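### The two CTCAE rules for toxicity conflict and neither fixes a version, and this one outcome counts only events attributed to TAE or MWA in a trial without double blinding

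*Combined protocol and SAP*

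**What the plan says.** The CTCAE outcome is described twice. In the secondary outcome list under Study Design, Objective, it is "Toxicity induced by TAE and or MWA using the latest published full version of Common Terminology Criteria for Adverse Events". The same bullet says that v5.0 is expected in October 2015 and that v4.0 is the version then available. Under Data Collection the text is "Toxicity induced by TAE and or MWA will be graded according to the" CTCAE v5.0, followed by the note "Slated for release in October 2015; v4.3 available at" and a web address.

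On blinding, Patient Eligibility and Allocation states: "The nature of the treatments and their possible adverse effects preclude the use of double-blind and double dummy techniques". No blinded assessor or adjudicator of toxicity is described anywhere.

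The plan has other safety measures. The outcome list includes "1-month and 3-month postoperative morbidity using the Clavien-Dindo Classification of Surgical Complications", mortality at 1 and 6 months, and readmission at 30 and 90 days. Postprocedural Strategy adds: "Postoperative complications will be recorded and treated symptomatically". Table 1 lists specific complications such as liver failure, ascites and encephalopathy. None of these is limited to events caused by the procedures.

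The Statistical Analysis section gives no method for summarizing or comparing toxicity between the arms.

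**The concern.** There are two separate weaknesses.

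The first is the scale. A grade has a fixed meaning only within one version of the criteria. One section lets the version float and the other names a version that did not yet exist, so two coders following the protocol could grade the same event differently. If the version changed during grading, counts by grade would combine different definitions and could not be pooled cleanly.

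The second is selection. An event enters this outcome only if someone decides that TAE or MWA caused it. That person may know the allocation, and the arms differ in the number of procedures to which an event can be attributed. A difference in readiness to attribute could therefore create or hide a difference in reported toxicity. This matters because the therapeutic benefit of the combination is described as unknown, so readers will want a sound account of what adding TAE does to adverse events.

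**Working it through.** The plan states no figure for toxicity, so there is none to reproduce. The check is a comparison of passages, plus two illustrations that rest on assumptions.

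**1. Version rules side by side**

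| | Secondary outcome list | Data Collection |
|---|---|---|
| Rule | newest full release | v5.0 |
| Status of v5.0 | expected October 2015 | expected October 2015 |
| Version available meanwhile | v4.0 | v4.3 |
| Version fixed for the trial | no | v5.0 named, but no rule for patients graded before it exists |
| Re-grading rule | none | none |

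The rules agree only if v5.0 is published before grading begins and nothing newer follows. Neither section says whether the newest release is judged at the event, at enrollment or at analysis.

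**2. How much mixing is possible**

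Inputs: 2 patients per month (Patient Eligibility and Allocation) and 100 patients (Sample Size). Accrual time = 100 / 2 = 50 months.

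Assumption: the version changes m months after the first enrollment, and each patient is graded on the version current at enrollment. The documents give neither a first-enrollment date nor an actual release date, so m is unknown. Patients on the older scale = 2 × m, out of 100:

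| m (months, assumed) | Older scale | Newer scale |
|---|---|---|
| 0 | 0 | 100 |
| 6 | 12 | 88 |
| 12 | 24 | 76 |
| 24 | 48 | 52 |
| 36 | 72 | 28 |

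A change at 6 to 12 months would put 12–24% of patients on the older scale, but nothing in the documents makes that window likelier than m = 0. Toxicity also occurs after enrollment, so if the version were chosen at each event the split would differ from this table.

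**3. Effect on the arm comparison**

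Under 1:1 blocked allocation both arms accrue together, so a change falls on them about equally. Unequal shares would need the 2:1 fallback in Sample Size as well as a version change. Illustration (assumption): 24 patients enrolled 1:1 on the older scale, then 83 − 24 = 59 enrolled 2:1 on the newer one. The later patients split about 39 and 20, giving arms of 51 and 32. The older-scale share is 12/51 = 24% in the combination arm and 12/32 = 38% in the MWA arm.

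**4. Attribution**

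Reported rate = true rate × proportion attributed to the procedures. Assumption, with no source in the documents: the true rate of grade 3 or higher is 20% in both arms, with 90% attributed in one arm and 70% in the other.

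- 0.20 × 0.90 = 18%, or 9 of 50 patients
- 0.20 × 0.70 = 14%, or 7 of 50 patients
- Spurious difference: 4 points, with the sign reversed if the proportions are swapped
- Standard error of the difference: √(0.18 × 0.82/50 + 0.14 × 0.86/50) = √0.00536 = 0.073, or about 7 points

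**5. Do the other safety outcomes fill the gap?**

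They need no attribution. But morbidity and mortality are labelled *postoperative*, and in the combination arm TAE starts within a week of randomization, with MWA planned 4 to 6 weeks later. The plan does not say which procedure starts the clock. If it is MWA, events between the two procedures, or in a patient who has TAE and never reaches MWA, fall outside those outcomes.

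**The case against.** The strongest reply is that this is one secondary outcome among several. Clavien-Dindo grade I in Appendix II takes in any departure from the expected course after surgery, and complications, deaths and readmissions are captured without asking about cause. Postprocedural Strategy follows all patients after both kinds of procedure. Reporting procedure-related toxicity beside such measures is a legitimate design. This stands, and it limits the attribution concern to the CTCAE outcome. What remains is the undefined start of the postoperative period.

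It is also fair to say that no between-arm toxicity test is specified, so there is no planned test to bias, and that the assumed 4-point distortion is smaller than its sampling error at 50 per arm. Both stand. They reduce the consequence, but a descriptive table by arm would still be read as a comparison.

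A reader might go further and infer three things that the documents do not support:

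- That early and late patients will be graded on different scales. This depends on dates and on a meaning of *latest* that are not given, and Data Collection names a single version.
- That a version change would bias the arm comparison. Under constant 1:1 blocks it would not do so to any material degree.
- That having TAE events in one arm only is itself a flaw. Only one arm receives TAE, and both arms can contribute MWA events.

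**Conclusion.** The point holds as a minor defect. The conflict between the two sections is certain and does not depend on any date: a floating version against v5.0, and v4.0 against v4.3 as the version in use meanwhile. Mixed scales are a possibility whose extent the documents do not allow anyone to estimate. It ranges from none to roughly half and half or beyond, according to an assumed date of change. It would chiefly hamper the pooling and reading of grades.

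Limiting the CTCAE outcome to events caused by the procedures, with no named assessor, criteria, time window or blinded review, lets unblinded judgment select its events. The direction and size of any effect are unknown, and the 18% versus 14% example shows only the mechanism. It would be wrong to conclude that attribution decides the safety results as a whole, because the other safety outcomes do not use it. They may, however, miss the interval between TAE and MWA.

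**What to change.** Name one published CTCAE version, in the same words, in the secondary outcome list and in Data Collection, and apply it to every patient for the whole trial.

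Add to Statistical Analysis that the CTCAE summary by arm covers all adverse events from randomization, whatever their attribution, counting each patient once at the worst grade. Report toxicity attributed to TAE or MWA in a separate descriptive table. Starting at randomization gives both arms the same time origin and brings in the interval between TAE and MWA.

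The cost is a few sentences of text, with no extra patients and no change in treatment, although adverse events must be recorded from randomization without an attribution filter. There are two drawbacks. Later updates of the scale go unused, and all-cause counts include background liver-disease events in both arms, which may dilute a real difference. The separate table of attributed events keeps the procedure-specific picture visible.

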with either an open, laparoscopic, or robot-assisted laparoscopic approach. **The expected enrollment rate is 2 patients/month.**

Patients diagnosed with primary HCC classified as stage 0 (very early) or stage A (early) will be considered for inclusion in this study. Tumors will be staged preoperatively with computed tomography (CT) and/or magnetic resonance imaging (MRI). Laparoscopic ultrasound will be performed intraoperatively.

Eligible patients will meet the following inclusion criteria:

- Male or female patients aged ≥ 18 and ≤ 75 years
- Primary diagnosis of HCC according to the guidelines published by the American Association for the Study of Liver Diseases (AASLD)²⁸ and the diagnostic criteria used by the European Association for the Study of the Liver (EASL)²⁹:
 - Two imaging techniques showing typical features of HCC; or
 - Cytologic/histologic diagnosis of HCC; or
 - Radiographic classification as LIRAD 5 (Appendix III), regardless of AFP level.
- HCC classification of stage 0 (very early) or stage A (early) according to BCLC staging system criteria (Appendix I):
 - Solitary HCC lesion < 3 cm in diameter
 - ≤ 3 HCC lesions, each ≤ 3.0 cm in diameter
- Total bilirubin level, with or without portal hypertension, less than or equal to 3.0.
- Adequate clinical condition to undergo laparoscopic or robot-assisted laparoscopic TAE and/or MWA as treatment for HCC
- Willing and able to give informed consent

Patients meeting the inclusion criteria will be subjected also to the following exclusion criteria:

- Radiologic (CT or MRI) evidence of invasion into major portal/hepatic venous branches and no extrahepatic metastases (LR-5V or LR-M radiologic classifications)
- Evidence of residual disease at first post-MWA CT examination
- Body Mass Index (BMI) > 35
- Previous history of hepatic resections
- Severe renal dysfunction (creatinine clearance of < 40 mL/min)

- Pregnant or nursing women

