Before randomization, patients will be assessed with either MRI or triphasic CT imaging and evaluated for baseline liver function, hematology, coagulation studies, and serum AFP. Liver function and underlying disease burden will be staged with the Child-Turcotte-Pugh criteria and the BCLC classification, respectively (Appendix IA and B). Radiologic findings will be reported according to the LI-RADS criteria. Patient demographics, histologic analysis, and assessment of portal vein hypertension and its sequelae will also be recorded. Patients will receive pre-operative counseling.

Carolinas Medical Center follows already established Enhanced Recovery After Surgery (ERAS) SMART™ protocol for the pre-, intra-, and postoperative care of patients undergoing certain procedures in the hepatopancreatobiliary Division. Division-specific standard guidelines will be applied to the care of patients included in this study.

Procedural Strategy

For MWA and TAE procedures, patients will be given general anesthesia. In patients randomized to receive the experimental therapy, TAE treatments will be initiated within one week of randomization, then followed by MWA within 4 to 6 weeks after reviewing radiological scans from TAE. MWA will be performed 4 to 6 weeks following randomization in standard MWA therapy groups. Treatment may be discontinued if any exclusion criteria develop in the patient or at the patient's request.

For TAE procedures, moderate/procedural or general anesthesia will be induced. A selective 5-F catheter will be introduced into the femoral vein, and visceral angiography will be performed to assess the arterial blood supply to the liver and to the lesion(s) identified on preprocedural imaging. All patients will undergo a distal super-selective catheterization of the hepatic arteries using a coaxial technique and microcatheters. Embolization will be performed with LC beads from BTG with a maximum size of 700 µm. The LC beads will be admixed with 8-15 mL of contrast and injected into the arterial branch at a rate of 1-2 mL/min. After embolization, angiography will be performed to determine the extent of vascular occlusion and to assess collateral tumor arterial supply. Patients will be observed carefully, and analgesia (morphine or meperidine) will be administered if necessary. Given the small tumor size included in this study, bilobar lesions will be treated sequentially during the same interventional procedure.

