APPENDIX IV: DIAGNOSTIC WORK-UP/PATHWAY

APPENDIX V: PERIOPERATIVE CARE PATHWAY FOR HCC

APPENDIX VI: PHARMACOKINETIC PARAMETERS OF LC Bead®

The LC Bead® is a preformed, deformable microsphere consisting of a biocompatible, sulphonate-modified, N-Fil hydrogel. LC Bead® comprise a range of hydrogel microspheres that are biocompatible, hydrophilic, nonresorbable and precisely calibrated. . The LC Bead® is available in 3 sizes ranging from 100µm to 700µm

PRESENTATION:

- Glass vial of 10ml
- Stopper sealed by an aluminum cap equipped with a colored cap
- Each vial contains approximately 1ml or 2ml of LC Bead® in a
- non-pyrogenic sterile physiological buffered saline.
- Each vial is intended for single patient use only. Do not resterilize. Discard any unused material

INDICATIONS:

LC Bead® microspheres are intended to be used for the embolization of hypervascular tumors and arteriovenous malformations (AVMs).

CONTRAINDICATIONS

1. Patients intolerant to occlusion procedures.
2. Vascular anatomy or blood flow that precludes catheter placement or emboli injection.
3. Presence or likely onset of vasospasm.
4. Presence or likely onset of hemorrhage.
5. Presence of severe atheromatous disease.
6. Presence of feeding arteries smaller than distal branches from which they emerge.
7. Presence of patent extra-to-intracranial anastomoses or shunts.
8. Presence of collateral vessel pathways potentially endangering normal territories during embolization.
9. Presence of end arteries leading directly to cranial nerves.
10. Presence of arteries supplying the lesion not large enough to accept LC Bead® microspheres.
11. Vascular resistance peripheral to the feeding arteries precluding passage of LC Bead® microspheres into the lesion.
12. Do not use LC Bead® microspheres in the following applications: Embolization of large diameter arteriovenous shunts (ie. where the blood does not pass through the arterial/capillary/venous transition but directly from artery to vein.
 - i. The pulmonary arterial vasculature.
 - ii. Any vasculature where the use of LC Bead® Embolic Agent could pass directly into the internal carotid artery or the above listed vessels.

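### The fitness criterion asks for TAE and/or MWA rather than both, and the embolic's listed contraindications are not tied to eligibility, so a patient unsuitable for TAE can be randomised

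*Combined protocol and SAP*

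**What the plan says.** **Eligibility.** Patient Eligibility and Allocation requires "Adequate clinical condition to undergo laparoscopic or robot-assisted laparoscopic TAE and/or MWA as treatment for HCC". The six exclusions concern venous invasion or metastasis, residual disease after ablation, BMI, earlier hepatic resection, renal function, and pregnancy or nursing. None refers to suitability for embolization.

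**Allocation and timing.** Eligible patients are randomised 1:1 to MWA + TAE or MWA alone. "In patients randomized to receive the experimental therapy, TAE treatments will be initiated within one week of randomization", and MWA follows. The discontinuation rule covers exclusion criteria that develop later and patient request.

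**The TAE procedure.** Procedural Strategy describes a catheter technique in which "visceral angiography will be performed to assess the arterial blood supply to the liver and to the lesion(s) identified on preprocedural imaging". The agent is fixed: "Embolization will be performed with LC beads from BTG with a maximum size of 700 µm".

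**The agent's contraindications.** Appendix VI describes that product and lists, among others, "Patients intolerant to occlusion procedures", "Presence of severe atheromatous disease" and "Vascular anatomy or blood flow that precludes catheter placement or emboli injection".

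**Work-up before randomisation.** Preprocedural Strategy calls for MRI or triphasic CT, liver function, haematology, coagulation studies, AFP and staging. It states no check that the patient is suitable for TAE.

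**Analysis.** Statistical Analysis specifies Kaplan–Meier estimates and a log-rank test by intention-to-treat. It does not say how a combination-arm patient who cannot have TAE is recorded or followed.

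**The concern.** Eligibility is settled before the arm is known, so each patient has to be suitable for whatever either arm may require. Here that means both procedures. A criterion met by fitness for one of them does not secure this. Describing TAE as laparoscopic compounds the problem, because the criterion then does not address fitness for the endovascular procedure the trial delivers.

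A patient with one of the listed contraindications can thus satisfy every written criterion and be allocated to TAE + MWA. If TAE is then not given, the patient stays in the combination arm with what amounts to control treatment, and the estimated effect shrinks. Feasibility of TAE + MWA is a secondary aim, and it is hard to interpret when suitability for TAE was never defined at entry.

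**Working it through.** **1. Do the criteria screen for TAE suitability?**

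| Item | Where | What it settles |
|---|---|---|
| Fitness criterion | Inclusion criteria | Met by fitness for TAE alone, MWA alone, or both |
| Needs of the two arms | Patient Eligibility and Allocation | Combination arm: TAE and MWA; control arm: MWA |
| Nature of TAE | Procedural Strategy | Catheter-based, not laparoscopic |
| Contraindications to the agent | Appendix VI | Listed, but not cited in the inclusion or exclusion criteria |
| Angiography | Procedural Strategy | Part of the TAE procedure, so after randomisation and in one arm |

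The wording fails in both directions. It admits a patient fit for MWA only, who cannot complete the combination arm, and a patient fit for TAE only, who cannot complete either arm.

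**2. The plan's own sample-size figure**

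Inputs from Sample Size: 80% versus 90% at 2 years, two-sided α = .05, 95% power, 92 evaluable (46 per arm), 100 enrolled (50 per arm). The two-proportion normal approximation with pooled null variance gives

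n per arm = [1.960·√(2·0.85·0.15) + 1.645·√(0.80·0.20 + 0.90·0.10)]² / 0.10² = (0.990 + 0.822)² / 0.01 ≈ 329, or 658 in total.

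The stated 92 is not reproduced. With the same formula, power is 26.7% at 46 per arm and 28.6% at 50 per arm. As a check against the planned log-rank test, the hazard ratio is ln 0.9 / ln 0.8 = 0.472. With 92 × 0.15 = 13.8 events, the Schoenfeld formula gives 28.6%. This shortfall is a separate problem and serves here only as the starting point.

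**3. Dilution from undelivered TAE**

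Let q be the share of the combination arm that cannot have TAE and has the control outcome of 80%. The documents give no value, so q is an assumption.

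Combination-arm rate = 0.90(1 − q) + 0.80q = 0.90 − 0.10q, and the difference from control = 0.10(1 − q).

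Power = Φ{[Δ√n − 1.960·√(2p̄(1 − p̄))] / √[p₁(1 − p₁) + p₂(1 − p₂)]}, where Δ is the difference, p̄ the mean of the two rates, p₁ = 0.80 and p₂ the combination-arm rate.

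| q | Combination rate | Difference (points) | Power, 46 per arm | Power, 50 per arm |
|---|---|---|---|---|
| 0 | 90.0% | 10.0 | 26.7% | 28.6% |
| 5% | 89.5% | 9.5 | 24.2% | 26.0% |
| 10% | 89.0% | 9.0 | 22.0% | 23.5% |
| 20% | 88.0% | 8.0 | 17.9% | 19.1% |

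Worked case, q = 10%, n = 46: Δ√n = 0.09 × 6.782 = 0.610; 1.960·√(2·0.845·0.155) = 1.003; denominator √(0.1600 + 0.0979) = 0.508. Then (0.610 − 1.003)/0.508 ≈ −0.773, and Φ = 22.0%.

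**4. How much could better wording recover?**

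Only cases identifiable before randomisation. Near q = 0 the loss is about 2.4 points for 5%, or roughly 0.5 point of power for each 1% of the arm. If only 1% to 2% were both unsuitable and identifiable in advance, that is 0.46 to 0.92 of a patient among 46, and about 0.5 to 1.0 point of power.

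**The case against.** **The wording may only be loose.** *And/or* could mean whichever regimen is assigned, and *laparoscopic* could be a misplaced modifier. Both are plausible, and the literal reading, which admits a patient fit for TAE alone, is unlikely to be what was intended. The text still does not state the intended meaning, and an eligibility rule has to work as written.

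**A check may exist elsewhere.** Division-specific guidelines are cited but not reproduced. In the text I could read, Appendices IV and V and Figure 1 survive only as titles. A TAE-suitability step could be there, which limits certainty. It would still not be a listed criterion.

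**A reader might infer that the protocol sends contraindicated patients to embolization.** The documents do not support that. Appendix VI is part of the protocol, angiography precedes embolization, and the centre reports several hundred TAE procedures a year. Nothing directs an operator to proceed against the list.

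**A reader might infer that arterial anatomy goes unexamined until after randomisation.** That also goes too far. MRI or triphasic CT comes first, and a comprehensive medical history is collected. What is missing is a rule for using that information, not the information itself.

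**A reader might infer selective dropout from one arm.** That would arise only if such patients were withdrawn, and the plan specifies intention-to-treat. The handling is unstated rather than wrong.

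**The effect is small.** This stands. The low baseline power comes from the sample-size calculation, and some Appendix VI items may be visible only at angiography.

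**Conclusion.** The point holds as a gap in the eligibility wording. The fitness criterion can be met by a patient who is unsuitable for TAE, and Appendix VI is not linked to eligibility, so such a patient can be randomised within the written rules. Under intention-to-treat the consequence is dilution towards no difference.

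The size is unknown. At an assumed 5% to 10% of the combination arm, with those patients taking the 80% control outcome, the planned difference loses 0.5 to 1.0 point, and power at 46 per arm drops by 2.4 to 4.7 points from 26.7%. This is an upper bound on what the change recovers, since cases first seen at angiography remain. It should not be read as explaining the trial's low power, nor as evidence that patients would be treated against a contraindication. The case for acting rests on the defect being plain in the text and very cheap to remove.

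**What to change.** 1. Reword the inclusion criterion, for example: *Judged before randomisation to be suitable for both catheter-based TAE and laparoscopic or robot-assisted laparoscopic MWA.*
2. Have the sponsor reconcile the eligibility list, Procedural Strategy and Appendix VI, and state how the protocol's own contraindications to the embolic bear on eligibility. Which items apply to this population is a clinical decision for the sponsor.
3. State in Statistical Analysis that a patient found unsuitable for TAE only at angiography stays in the allocated arm for the intention-to-treat analysis. Report the number and reasons by arm as part of the feasibility results.

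**Cost.** A short amendment that draws on imaging and history the protocol already collects. A few TAE-unsuitable patients would no longer be enrolled, which slightly narrows the population to which the feasibility aim applies.
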